5.2.2 Occurrence of adverse events by CTCAE Grade (the worst one)

(1) Analysis sets to be used

Safety analysis set, safety analysis set (Hodgkin’s lymphoma), and safety analysis set (anaplastic large-cell lymphoma)

(2) Data to be analyzed

For each data item, patients will be stratified into the following categories, and the type of adverse events will be analyzed:

Data item	Category
CTCAE Grade (the worst one)	≤Grade 2, ≥Grade 3, or unknown

The type of adverse events will be analyzed as follows:

Data item	Data to be analyzed
Type of adverse events	The incidence of adverse events for each CTCAE grade (the worst one) will be calculated by SOC and PT. For SOC, the number and percentage of patients with adverse events will be calculated. For PT, the number and percentage of adverse events will be calculated. SOCs will be presented in the internationally

	agreed order, and PTs will be presented in ascending order of HLGT and PT codes if their SOCs are “Investigations,” and in ascending order of PT code otherwise. The CTCAE grade (the worst one) is higher in the order of \geq Grade 3, \leq Grade 2, and unknown. If the same patient has multiple occurrences of the same adverse event (PT), the event with the highest CTCAE grade will be counted once per patient.
--	---

(3) Figure/table number

Tables 5.2.2-1 to 5.2.2-3

5.2.3 Seriousness, CTCAE Grade (the worst one), time of onset, time to the worst grade, and occurrence of adverse drug reactions/infections by outcome

(1) Analysis sets to be used

Safety analysis set, safety analysis set (Hodgkin’s lymphoma), and safety analysis set (anaplastic large-cell lymphoma)

(2) Data to be analyzed

For each data item, patients will be stratified into the following categories, and the type of adverse drug reactions, etc., will be analyzed:

Data item	Category
Seriousness	Serious or non-serious
CTCAE Grade (the worst one)	Grade 1, Grade 2, Grade 3, Grade 4, Grade 5, or unknown
Time of onset	1 to 7 days, 8 to 14 days, 15 to 21 days, 22 to 84 days, 85 to 168 days, 169 to 252 days, 253 to 336 days, ≥ 337 days, or unknown
	1 to 21 days, 22 to 42 days, 43 to 63 days, (segmented similarly using a 21-day time window thereafter), 316 to 336 days, ≥ 337 days, or unknown
Time to the worst grade	1 to 7 days, 8 to 14 days, 15 to 21 days, 22 to 84 days, 85 to 168 days, 169 to 252 days, 253 to 336 days, ≥ 337 days, or unknown
	1 to 21 days, 22 to 42 days, 43 to 63 days, (segmented similarly using a 21-day time window thereafter), 316 to 336 days, ≥ 337 days, or unknown
Outcome	Recovered/resolved, recovering/resolving, not recovered/not resolved, recovered/resolved with sequelae, died/fatal, unknown, or not provided

The type of adverse drug reactions, etc., will be analyzed as follows:

Data item	Data to be analyzed
Number of patients	Number of patients with adverse drug reactions, etc., by SOC/PT If the same patient has multiple occurrences of the same adverse drug reactions, etc. (PT), all these occurrences will be counted (i.e., the overlap should be reflected).
Number of adverse drug reactions, etc.	Number of adverse drug reactions, etc., observed by SOC/PT
Seriousness, CTCAE Grade (the worst one), time of onset, time to the worst grade, and outcome	The number of adverse drug reactions, etc., will be calculated by SOC and PT. SOC’s will be presented in the internationally agreed order, and PT’s will be presented in ascending order of HLGTT and PT codes if their SOC’s are “Investigations,” and in ascending order of PT code otherwise. If the same patient has multiple occurrences of the same adverse drug reaction, etc. (PT), the total number of occurrences will be

	calculated per category (for example, if the same patient has one episode of serious diarrhea and one episode of non-serious diarrhea, these adverse drug reactions will be counted once for each category). If the same patient has multiple occurrences of the same adverse drug reaction, etc., classified into the same category, all these occurrences will be counted (i.e., the overlap should be reflected).
--	--

(3) Figure/table number

Tables 5.2.3-1 to 5.2.3-3

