Serious adverse events	
Adverse events considered “serious” by the investigator.
 
Events listed in the MedDRA Coding List in the Takeda Medically Significant AE List should be regarded as serious even if they are considered “non-serious” by the investigator.

Number of patients with adverse events/adverse drug reactions	Number of patients experiencing adverse events or adverse drug reactions, etc.
Number of adverse events/adverse drug reactions	Number of adverse events or adverse drug reactions, etc., observed
Percentage of patients with adverse events/adverse drug reactions	
[For safety analysis using patients included in the safety analysis set]
 
Is calculated using the following formula: (number of patients with adverse events/adverse drug reactions) / (number of patients included in the safety analysis set) × 100.
 
[For safety analysis using patients excluded from the safety analysis set]
 
Is calculated using the following formula: (number of patients with adverse events/adverse drug reactions) / (number of patients excluded from the safety analysis set) × 100.

Percentage of adverse events/adverse drug reactions observed	
[For safety analysis using patients included in the safety analysis set]
 
Is calculated using the following formula: (number of adverse events/adverse drug reactions observed) / (number of patients included in the safety analysis set) × 100.
 
[For safety analysis using patients excluded from the safety analysis set]
 
Is calculated using the following formula:(number of adverse events/adverse drug reactions observed) / (number of patients excluded from the safety analysis set) × 100.

Time of onset	
Is calculated using the following formula: date of onset of adverse events (or adverse drug reactions, etc.) – date of the initial dose of Adcetris + 1.
 
If the day, month, and year of onset of adverse events (or adverse drug reactions, etc.) are unknown, the time of onset should be handled as missing, and the category for the time of onset should be “unknown.”

Time to the worst grade	Is calculated using the following formula: date of the worst CTCAE grade – date of the initial dose of Adcetris + 1.

Term	Definition																									
	If the day, month, and year of the worst CTCAE grade are unknown, the date of the worst CTCAE grade should be handled as missing, and the category for the date of the worst CTCAE grade should be “unknown.”																									

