	1 to 21 days, 22 to 42 days, 43 to 63 days, (segmented similarly using a 21-day time window thereafter), 316 to 336 days, ≥ 337 days, or unknown
Time to the worst grade	1 to 7 days, 8 to 14 days, 15 to 21 days, 22 to 84 days, 85 to 168 days, 169 to 252 days, 253 to 336 days, ≥ 337 days, or unknown
	1 to 21 days, 22 to 42 days, 43 to 63 days, (segmented similarly using a 21-day time window thereafter), 316 to 336 days, ≥ 337 days, or unknown
Outcome	Recovered/resolved, recovering/resolving, not recovered/not resolved, recovered/resolved with sequelae, died/fatal, unknown, or not provided

The type of adverse events will be analyzed as follows:

Data item	Data to be analyzed
Number of patients	Number of patients with adverse events by SOC/PT
Number of adverse events, etc.	Number of adverse events observed by SOC/PT If the same patient has multiple occurrences of the same adverse event (PT), all these occurrences will be counted (i.e., the overlap should be reflected).
Seriousness, CTCAE Grade (the worst one), time of onset, time to the worst grade, and outcome	The number of adverse events will be calculated by SOC and PT. SOCs will be presented in the internationally agreed order, and PTs will be presented in ascending order of HLGT and PT codes if their SOCs are “Investigations,” and in ascending order of PT code otherwise. If the same patient has multiple occurrences of the same adverse event (PT), the total number of occurrences will be calculated per category (for example, if the same patient has one episode of serious diarrhea and one episode of non-serious diarrhea, these events will be counted once for each category). If the same patient has multiple occurrences of the same adverse event classified into the same category, all these occurrences will be counted (i.e., the overlap should be reflected).

(3) Figure/table number

Tables 5.2.1-1 to 5.2.1-3

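### SAP 5.2.3 puts the rule to count every repeat occurrence in the patients row, so a patient with repeats of one PT is counted more than once there

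*SAP*

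**What the plan says.** The section at issue is 5.2.3 of the SAP that opens the file, the one with a section defining the analysis sets. Its table has a row for patients, a row for reactions, and a row for the breakdowns.

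- **Patients row.** The count and the repeat rule stand in one cell: "Number of patients with adverse drug reactions, etc., by SOC/PT If the same patient has multiple occurrences of the same adverse drug reactions". The rule itself is: "If the same patient has multiple occurrences of the same adverse drug reactions, etc. (PT), all these occurrences will be counted". The instruction ends: "all these occurrences will be counted (i.e., the overlap should be reflected".
- **Reactions row.** This cell holds only "Number of adverse drug reactions, etc., observed by SOC/PT", with no rule for repeats.
- **Breakdown row.** Seriousness, grade, onset, time to worst grade and outcome are specified as numbers of reactions, with all repeats counted.

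In the sister table for adverse events, 5.2.1, the patients row holds only "Number of patients with adverse events by SOC/PT" and the rule is in the events row: "Number of adverse events observed by SOC/PT If the same patient has multiple occurrences of the same adverse event (PT), all these occurrences".

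The definitions table in SAP section 1 defines the patient count as "Number of patients experiencing adverse events or adverse drug reactions, etc".

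**The concern.** A patient count and an event count answer different questions. A safety table shows both so that the reader can tell many patients with one episode from a few patients with many. If the patients row follows the rule written in it, that distinction is lost for any PT that recurs.

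Recurrence is to be expected. Observation runs over as many as 16 cycles, and SAP 5.9.8 and 5.9.9 provide for several occurrences of neutropenia in one patient. The coding rules also make repeats of a single PT more likely: infusion reactions all go to one PT, entries in the peripheral nerve disorder field go to three, and decreased neutrophil count is merged into neutropenia.

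At stake is the patient-count entry for each SOC and PT in Tables 5.2.3-1 to 5.2.3-3. It would be overstated wherever a PT recurs, and would conflict with other tables built from the same data.

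**Working it through.** The plan states no figure for this point, so there is none to reproduce. The check compares the passages and then counts the SAP's own example.

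**Step 1: where the rule stands.**

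| Place | Patients row | Events or reactions row |
|---|---|---|
| SAP 5.2.3 (reactions) | Rule present | No rule |
| SAP 5.2.1 (events) | No rule | Rule present |
| Supplemental SAP 2.1 (September 15, 2017) | No rule | Rule present |
| 5.2.3 in the other SAP version that splits the safety set by diagnosis | No rule | No rule |

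Only the 5.2.3 under review attaches the rule to patients. In SAP 5.1.2, the type-of-reaction row counts a repeated PT once per patient.

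**Step 2: what the literal rule counts.** Let patient i have k_i occurrences of a given PT.

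- Correct patient count: N = number of patients with k_i ≥ 1.
- Event count: E = sum of the k_i.
- Patients row as written: every occurrence is counted, so the entry is the sum of the k_i, which is E.
- Excess: E − N = sum of (k_i − 1) over the affected patients. It is zero only if nobody has a repeat.

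**Step 3: the SAP's example.** Section 5.2.3 describes one patient with one serious and one non-serious episode of diarrhea, so k = 2.

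| Placement of the rule | Patients | Reactions |
|---|---|---|
| As written in 5.2.3 | 2 | 2 |
| Moved to the reactions row | 1 | 2 |

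**Step 4: what else depends on the rule.**

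- The 5.2.3 breakdowns are event counts by design and do not change.
- 5.1.2 counts a repeated PT once per patient in its type-of-reaction row.
- 5.2.4 counts the highest grade of a repeated PT once per patient.
- 5.3 uses the percentage of patients with any reaction.
- 5.2.3 itself specifies no percentage, confidence interval or test.

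The effect stops at the patient-count entries of Tables 5.2.3-1 to 5.2.3-3.

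**The case against.** The strongest reply is that this is a clerical slip whose intent is plain. The cell still opens as a count of patients, the definition says patients, and the parallel tables show where the sentence belongs. A careful programmer would probably produce the right number. That stands as an account of the cause and is a reason to rate the point low. It does not remove the point: the instruction is explicit, so producing the right count means departing from the written plan.

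A second reply is that Supplemental SAP 2.1, under a title about adverse drug reactions, already has the rule in the right row. But its body text speaks of adverse events, it changes the counting for grade and time to worst grade, and it does not say that it replaces 5.2.3. It supports the intended reading without clearly curing the error.

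A third is that the text was read from PDF and a row may have shifted. This cannot be excluded. It is unlikely, because the sentence comes before the next row label and 5.2.1 was read with the same sentence in its events row.

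It is also true that the reactions count is not left undefined. The reactions cell has no repeat rule, but the definitions, 5.1.2 and the breakdown row of 5.2.3 all make it a count of every occurrence.

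**Conclusion.** The rule is wrong as written. On a literal reading, a patient with k occurrences of one PT adds k to the patient count in Tables 5.2.3-1 to 5.2.3-3, so for PTs with repeats that count equals the event count. The conclusion assumes only that some patients have repeats of a PT and that the rule is applied as it stands.

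Two stronger readings are not supported.

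- A reader might infer that the survey's main reaction results are inflated. They are not: the patient-level results come from 5.1.2, 5.2.4 and 5.3, and the 5.2.3 breakdowns are meant to be event counts.
- A reader might try to size the inflation from the protocol's 20% for neutropenia: 0.20 × 140 = 28 patients, multiplied by an assumed 1.3 to 1.5 episodes each, giving 36 to 42. The 20% is for Grade 3 or higher neutropenia in non-Japanese phase 2 studies, whereas 5.2.3 covers related events of all grades in this survey. No document gives an episode rate, so the size cannot be estimated.

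Severity: minor. It is an internal inconsistency confined to one row of one set of tables.

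**What to change.** Move the sentence on repeat occurrences from the number-of-patients row of SAP 5.2.3 to the number-of-reactions row, matching 5.2.1. In the patients row, state that each patient is counted once per SOC and once per PT.

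If Tables 5.2.3-1 to 5.2.3-3 have already been produced, compare their patient counts with the once-per-patient PT counts in the tables of 5.1.2. Both sections use the same three analysis sets and the same PT replacements, so the comparison is like for like. Any PT whose 5.2.3 count is higher has been affected.

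The cost is one sentence moved, one added and, where output exists, a short reconciliation. No data collection or other analysis changes.

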5.2.4 Occurrence of adverse drug reactions/infections by CTCAE Grade (the worst one)

(1) Analysis sets to be used

Safety analysis set, safety analysis set (Hodgkin’s lymphoma), and safety analysis set (anaplastic large-cell lymphoma)

(2) Data to be analyzed

For each data item, patients will be stratified into the following categories, and the type of adverse drug reactions, etc., will be analyzed:

Data item	Category
CTCAE Grade (the worst one)	≤Grade 2, ≥Grade 3, or unknown

The type of adverse drug reactions, etc., will be analyzed as follows:

Data item	Data to be analyzed
Type of adverse drug reactions, etc.	The incidence of adverse drug reactions, etc., for each CTCAE grade (the worst one) will be calculated by SOC and PT. For SOC, the number and percentage of patients with drug reactions, etc., will be calculated. For PT, the number and percentage of drug reactions, etc., will be calculated. SOCs will be presented in the internationally agreed order, and PTs will be presented in ascending order of HLGT and PT codes if their SOCs are “Investigations,” and in ascending order of PT code otherwise. The CTCAE grade (the worst one) is higher in the order of ≥Grade 3, ≤Grade 2, and unknown. If the same patient has multiple occurrences of the same adverse drug reaction, etc. (PT), the reaction with the highest CTCAE grade will be counted once per patient.

(3) Figure/table number

Tables 5.2.4-1 to 5.2.4-3

5.3 Percentage of patients with adverse drug reactions/infections by patient demographics and baseline characteristics and treatment given

(1) Analysis sets to be used

Safety analysis set, safety analysis set (Hodgkin’s lymphoma), and safety analysis set (anaplastic large-cell lymphoma)

(2) Data to be analyzed

For each data item, patients will be stratified into the following categories, and the percentage of patients with adverse drug reactions, etc. (with point estimate and 95% confidence interval) will be determined.

For categories associated and not associated with ranking, Fisher’s exact and Mann-Whitney U tests, respectively, will be used. If there is a category of “unknown,” it will be excluded to perform

the Mann-Whitney U test.

Data item	Category
Sex	Male or female
Age	<18 years, 18 to 64 years, 65 to 74 years, or ≥ 75 years
Disease duration	<1 year, <1 to 3 years, <3 to 5 years, ≥ 5 years, or unknown
ALK (for patients with anaplastic large-cell lymphoma)	Positive, negative, or unknown
Clinical stage	I, II, III, IV, or unknown
B symptoms	Absent or present
ECOG Performance Status	0, 1, 2, 3, or 4
Past history of pulmonary disorders	Absent or present
Concurrent pulmonary disorders	Absent or present
Past history of malignant tumours	Absent or present
Concurrent malignant tumours	Absent or present
Concurrent hepatic disorders	Absent or present
Grade of hepatic disorder (Grade based on AST and ALT levels)	None, Grade 1, Grade 2, \geq Grade 3, or unknown
Concurrent renal disorders	Absent or present
Grade of renal disorder (Grade based on serum creatinine)	None, Grade 1, Grade 2, \geq Grade 3, or unknown
Weight	<40 kg, <40 to 50 kg, <50 to 60 kg, <60 to 70 kg, or ≥ 70 kg
BMI	<18.5 kg/m ² , <18.5 to 25 kg/m ² , <25 to 30 kg/m ² , or ≥ 30 kg/m ²
Smoking history	Never, current, past, or unknown
Prior drug therapy	Absent or present
Prior radiotherapy	Absent or present
Prior hematopoietic stem cell transplantation	Absent, present (autologous), present (homologous), present (autologous and homologous), or unknown
Initial dose of Adcetris	<1.2 mg/kg, 1.2 mg/kg, >1.2 mg/kg to <1.8 mg/kg, 1.8 mg/kg, or >1.8 mg/kg

Data item	Category
Mean dose of Adcetris	<1.2 mg/kg, 1.2 mg/kg, >1.2 mg/kg to <1.8 mg/kg, 1.8 mg/kg, or >1.8 mg/kg
Dose of Adcetris per 3 weeks	<1.2 mg/kg, 1.2 mg/kg, >1.2 mg/kg to <1.8 mg/kg, 1.8 mg/kg, or >1.8 mg/kg
Drug(s) other than Adcetris used for the treatment of the primary disease	Absent or present

(3) Figure/table number

Tables 5.3-1 to 5.3-3

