**Table 1 Definition of an Adverse Event**

An adverse event (AE) is any untoward or undesirable medical occurrence in a patient linked in time with the use of a pharmaceutical/ medicinal product and which does not necessarily have to have a causal relationship with this treatment or may or may not be considered related to the product. An adverse event can therefore be any unfavorable and unintended sign (including an abnormal laboratory finding), symptom, or disease temporally associated with the use of a medicinal product, whether or not related to the medicinal product.

Adverse events also include:

- Symptoms observed in an infant breast-fed by a mother receiving treatment with Adcetris.

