#### 10.4.2 Factors that may affect the safety of Adcetris

The frequency of adverse events observed during the observation period will be analyzed by patient background factors (sex, age, presence/absence of concurrent renal disorders, and presence/absence of concurrent hepatic disorders) and treatment given (the status of treatment with Adcetris and concomitant medications).

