1.1.2 Efficacy analysis set

In this survey, the efficacy analysis set is defined as patients treated with Adcetris IV Infusion with no major protocol violation and evaluable for efficacy.

Definition

Term	Definition
This/the product	Refers to Adcetris for intravenous drip infusion in this Statistical Analysis Plan.
SOC	MedDRA/J System Organ Class
HLGT	MedDRA/J High Level Group Term
PT	MedDRA/J Preferred Term
LLT	MedDRA/J Lowest Level Term
Patients registered	Patients whose registration has been approved
Patients whose case report forms are available	Patients whose case report forms have been collected
Patients whose case report forms are not available	Patients registered but whose case report form have not been collected
Fixed patients	Patients whose case report forms are available, with the date of case report form completion entered in the PMS system
Non-fixed patients	Patients whose case report forms are available, with the date of case report form completion not entered in the PMS system
Safety analysis set	Fixed patients included in the safety analysis set
Safety analysis set (Hodgkin's lymphoma)	Patients included in the safety analysis set whose diagnosis is Hodgkin's lymphoma
Safety analysis set (anaplastic large-cell lymphoma)	Patients included in the safety analysis set whose diagnosis is anaplastic large-cell lymphoma
Patients excluded from the safety analysis set	Fixed patients excluded from the safety analysis set
Efficacy analysis set	Patients included in the safety analysis set who are also included in the efficacy analysis set
Patients excluded from the efficacy analysis set	Patients included in the safety analysis set who are excluded from the efficacy analysis set
Patients completing treatment	Patients completing 16 cycles of treatment with Adcetris
Patients discontinuing treatment	Patients not completing 16 cycles of treatment with Adcetris

Term	Definition
Adverse drug reactions, etc.	
Refers to “adverse drug reactions and infections.”
 
Adverse events not considered “not related” to Adcetris by the investigator.
 
In this Statistical Analysis Plan, the term “adverse drug reactions and infections” is used in titles and the term “adverse drug reactions, etc.” is used in text and tables.

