5.4 Occurrence of adverse drug reactions/infections by age group

(1) Analysis sets to be used

Safety analysis set, safety analysis set (Hodgkin's lymphoma), and safety analysis set (anaplastic large-cell lymphoma)

(2) Data to be analyzed

The similar calculation as the one described in Section 5.1.2, will be performed by age group (<18 years, 18 to 64 years, 65 to 74 years, or ≥ 75 years).

The type of adverse drug reactions, etc., will be analyzed in the same manner as described in Section 5.1.

(3) Figure/table number

Tables 5.4-1 to 5.4-3

5.5 Occurrence of adverse drug reactions/infections by presence or absence and grade of concurrent hepatic disorder

(1) Analysis sets to be used

Safety analysis set, safety analysis set (Hodgkin's lymphoma), and safety analysis set (anaplastic large-cell lymphoma)

(2) Data to be analyzed

The similar calculation as the one described in Section 5.1.2, will be performed by presence or absence and grade of concurrent hepatic disorder.

The type of adverse drug reactions, etc., will be analyzed in the same manner as described in Section 5.1.

(3) Figure/table number

Tables 5.5-1 to 5.5-3

5.6 Occurrence of adverse drug reactions/infections by presence or absence and grade of concurrent renal disorder

(1) Analysis sets to be used

Safety analysis set, safety analysis set (Hodgkin's lymphoma), and safety analysis set (anaplastic large-cell lymphoma)

(2) Data to be analyzed

The similar calculation as the one described in Section 5.1.2, will be performed by presence or absence and grade of concurrent renal disorder

The type of adverse drug reactions, etc., will be analyzed in the same manner as described in Section 5.1.

(3) Figure/table number

Tables 5.6-1 to 5.6-3

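### Protocol 10.4.2 calls for adverse events of any cause by sex, age, renal and hepatic disorder and treatment given; SAP 5.3–5.6 tabulate only adverse drug reactions by these factors, and no reason is given

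*SAP*

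**What the plan says.** Protocol 10.4.2, headed as factors that may affect the safety of Adcetris, states: "The frequency of adverse events observed during the observation period will be analyzed by patient background factors". The factors are sex, age, presence or absence of renal disorder, and then "presence/absence of concurrent hepatic disorders) and treatment given (the status of treatment with Adcetris and concomitant medications". Protocol Table 1 makes an adverse event an all-cause term: an occurrence "temporally associated with the use of a medicinal product, whether or not related to the medicinal product".

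SAP 5.3 covers the same ground with a narrower outcome: "the percentage of patients with adverse drug reactions, etc. (with point estimate and 95% confidence interval) will be determined". The definitions in SAP section 1 limit that outcome to "Adverse events not considered “not related” to Adcetris by the investigator". SAP 5.4 reads "The similar calculation as the one described in Section 5.1.2, will be performed by age group", and SAP 5.5 reads "The similar calculation as the one described in Section 5.1.2, will be performed by presence or absence and grade of concurrent hepatic disorder"; 5.6 does the same for renal disorder. Section 5.1.2 is the adverse-drug-reaction table. The all-cause table is 5.1.1.

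**The concern.** The protocol names one outcome for its factor analysis and the SAP analyses a subset of it. An analyst who follows the SAP exactly will not produce what 10.4.2 specifies, in a study whose stated purpose is safety in routine care.

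There is a second, weaker reason to care. Protocol Table 3 lets an investigator call an event not related when it is very likely due to the primary disease, a concurrent illness or a concomitant therapy. Hepatic disorder, renal disorder and other lymphoma drugs are themselves factors in 10.4.2. For these, the rule that removes events from the count may depend on the factor being studied, and a comparison of adverse drug reactions alone cannot show whether it did.

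**Working it through.** The plan gives no figure to reproduce here. The check is a comparison of texts, followed by three small counts.

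**Step 1: which tables count which events, and how patients are divided.**

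| Place | Events counted | Patients divided by |
|---|---|---|
| Protocol 10.4.2 | Adverse events, any cause | Sex, age, renal disorder, hepatic disorder, Adcetris treatment, concomitant medications |
| SAP 5.1.1 | Any cause | Lymphoma type only |
| SAP 5.2.1, 5.2.2 | Any cause | Lymphoma type only (events split by seriousness, grade, timing or outcome) |
| SAP 5.7 | Serious, any cause | Lymphoma type only |
| SAP 5.3 | Adverse drug reactions | 25 background and treatment rows |
| SAP 5.4, 5.5, 5.6 | Adverse drug reactions | Age; hepatic disorder and grade; renal disorder and grade |
| SAP 5.9.2, 5.9.5–5.9.7, 5.9.13 | Events of one kind considered related | Selected factors |
| First supplement | 2.1: event attributes; 2.2: related infections after neutropenia or lymphopenia | None of the 10.4.2 factors |
| Second supplement | Related neutropenia | Transplant history, baseline neutrophils, infection prophylaxis; action taken and outcome |

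Of the four SAP sections that apply the 10.4.2 factors to overall safety (5.3–5.6), none uses all-cause events. The mismatch does not come from one revision: 10.4.2 reads the same in all five protocol versions in the file, and 5.3–5.6 count adverse drug reactions in all three versions of the main SAP.

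**Step 2: rows of SAP 5.3 that answer to 10.4.2.** Sex 1 + age 1 + presence of hepatic disorder 1 + presence of renal disorder 1 + dose rows 3 (initial, mean, per 3 weeks) + the row "Drug(s) other than Adcetris used for the treatment of the primary disease" 1 = 8. The other 25 − 8 = 17 rows, including the two laboratory-grade rows, are SAP additions.

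**Step 3: tables needed.** Protocol 10.4 names only the safety analysis set. Four sections (5.3, 5.4, 5.5, 5.6) × 1 set = 4 tables.

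**Step 4: what is lost, and what bounds it.** Only events judged not related leave the count. Indeterminate events stay, as do events with other contributing causes where Adcetris is also likely. Let D be the number of patients with an adverse event but no adverse drug reaction, that is, the patient count in 5.1.1 minus that in 5.1.2. Patients with a reaction are a subset of patients with an event, so in 5.3 a level of m patients can lose at most min(D, m)/m of its percentage. This is 0 when D = 0, and it reaches 1, and so says nothing, when D ≥ m. The documents give neither D nor m, so no size can be computed. No planned table shows how D divides between the levels of a factor.

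**The case against.** The best defence is that adverse drug reactions are the more drug-specific outcome. There is no control group, so all-cause rates by comorbidity or co-therapy also count events produced by those conditions. The reaction definition is broad, protocol 9.2.5 requires the rationale for each not-related judgement to be collected, 5.1.1 against 5.1.2 shows the overall removal by SOC and PT, and 5.7 shows the not-related serious events. Consistent wording across SAP versions could reflect a settled choice. All of this supports keeping the present tables. It does not supply the ones that 10.4.2 names. Loose terminology is not an answer either: the protocol writes of adverse drug reactions when it means them (14.1), and the SAP pairs all-cause and reaction tables elsewhere (5.1.1 with 5.1.2, 5.2.1 with 5.2.3, 5.2.2 with 5.2.4). The cross-reference in 5.4–5.6 to the manner of Section 5.1 does not bring in all-cause events, because its subject is the type of adverse drug reactions.

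The mapping in Step 2 can also be questioned. A wide reading of treatment status and concomitant medications could take in number of cycles, infection prophylaxis and premedication, which SAP 4.1 and 4.2 tabulate. The eight rows are those that SAP 5.3 itself offers for these factors.

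A reader might infer more than the documents support:

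- That the restriction hides a hepatic, renal or co-therapy signal. No not-related shares are given; equal attribution across levels would remove any distortion, and unequal attribution could act in either direction.
- That the same mechanism reaches sex or age. Table 3 mentions neither.
- That laboratory grades, the lymphoma-type subsets, or all-cause columns in 5.9.2 and 5.9.13 are also owed. Protocol 10.4.2 names only presence or absence of the two disorders, and 10.4 names only the overall safety set.

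**Conclusion.** The point stands as a departure of the SAP from the protocol. The all-cause factor analysis in 10.4.2 is not planned anywhere, and no text explains why. This conclusion rests on wording alone and needs no assumption about data. Its extent is 8 rows of 5.3 and the age, hepatic-presence and renal-presence splits of 5.4–5.6.

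The consequence for interpretation is a possibility only, confined to hepatic disorder, renal disorder and co-therapy. Its size is unknown and may be nil. The case for change is therefore the undelivered analysis and its low cost, not a demonstrated bias.

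**What to change.** In the overall safety analysis set, add all-cause versions of:

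- the eight matching rows of SAP 5.3: sex, age, presence or absence of hepatic disorder, presence or absence of renal disorder, the three dose rows, and other drugs for the primary disease;
- SAP 5.4 by age, and 5.5 and 5.6 by presence or absence of hepatic and renal disorder.

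Keep them descriptive, with counts, percentages and 95% confidence intervals and no added p-values, and set them beside the adverse-drug-reaction tables, which stay. State in the SAP that all-cause counts include events caused by the comorbidity or co-therapy itself, so that neither version is read alone.

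Optional, and not required by 10.4.2: lymphoma-type subsets, laboratory-grade splits, the share judged not related at each level, and all-cause columns in 5.9.2 and 5.9.13.

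The cost is four descriptive tables from data already collected and a short SAP wording change. Recording a reason for using adverse drug reactions alone would be cheaper and would end the silence, but it would still leave 10.4.2 undelivered.
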